6.4. Safety Evaluation

Safety analysis will be performed on the Safety Set and will be reported by actual treatment group. No methodology for missing data handling will be applied for safety parameters.

6.4.1. Extent of Exposure

The exposure to the study treatment will be evaluated by means of the variables defined below.

The following definitions will be applied in the variable calculation:

- First drug administration: it is the earliest date when a non-zero dose of study treatment was administered and recorded on the eCRF.
- Last drug administration: it is the latest date when a non-zero dose of study treatment was administered and recorded on the eCRF.

The duration of exposure to study treatment is calculated as:

Duration of exposure (days) = (Date of Last drug administration - Date of First drug administration + 1).

The duration of exposure to study treatment includes the periods of temporary interruption of the study treatment for any reason.

The duration of actual exposure to study treatment will be calculated excluding the periods of temporary interruption of the study treatment for any reason.

Ver.04 25Jun2020

Sponsor: ITALFARMACO Protocol: DSC/15/2357/53

The total daily dose in mg (i.e. mL X 10 = mg) will be calculated as the total amount of drug administered during the study divided by the duration of actual exposure.

The duration of exposure to study treatment, the duration of actual exposure to study treatment and the total daily dose will be summarized by means of the usual descriptive statistics on the Safety Analysis Set overall and by treatment group.

The number and percentage of subjects with and without any IMP modification, as well as the number and percentage of subjects with each type of IMP modification (dose increased, dose reduced, dose permanently stopped, dose temporarily stopped) and the reason for the modification (Adverse event/Lab or ECG abnormality, dosing error, other) will be summarized by treatment group.

6.4.2. Concomitant medications

Prior (i.e. medications ended before first intake), concomitant (i.e. medications started before first intake and ongoing at the baseline) and steroid medications (used at baseline) will be presented as the number and percentages of patients with at least one prior/concomitant/steroid medication. Prior concomitant and steroid medication will be also classified using the WHO-DRL drug dictionary (using the most recent version) and summarized overall by WHO Anatomical Therapeutic Chemical /ATC) Class and Preferred Term.

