### 8.7.2 Prior and Concomitant Medications

All medications and other treatments taken by the patient during the study, including those treatments initiated within 6 months prior to the start of the study, must be recorded on the eCRF.

Concomitant treatments are defined as treatments taken after study treatment administration. Any medication or therapy that is taken by or administered to the patient during the study must be recorded in the eCRF. The entry must include dose, regimen, route, indication, and dates of use.

After the Screening visit, medication to treat minor treatment-emergent illnesses are generally permitted; supportive treatments such as antiemetics, antidiarrheals, antipyretics, anti-allergics, analgesics and antibiotics are allowed.

Use of Vitamin D, calcium and any other supplements if clinically indicated before enrollment and for the duration of the study is allowed

The following therapies are expressly prohibited throughout the study:

- Any other investigational drug while on this study.
- Any dystrophin restoration product.
- Any pharmacologic treatment, other than corticosteroids, that might have an effect on muscle strength or function (e.g., growth hormone).

The following are concomitant therapy requiring caution throughout the study:

 Drugs known to increase the QT interval (see Appendix 16.1 for a list of such compounds).

17 June 2020 Page 58 of 110

- Live or live attenuated vaccines: the patient must be carefully monitored. While the
  decision of the Investigator cannot be influenced, rejected nor approved by the
  Medical Monitor, it is advised but not mandatory that the Investigator discuss the case
  with the Medical Monitor before using these vaccines.
- Drugs known to be a substrate of Organic Cation Transporter 2 (see Appendix 16.2 for a list of such compounds).
- Antiplatelet, thrombolytic or anticoagulant drugs must be carefully monitored.
- Drugs known to be P-glycoprotein inhibitors (see Appendix 16.3 for a list of such compounds).

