# 13.5 Prior and Concomitant Therapy

Prior treatments, defined as those taken within 6 months prior to screening, should be recorded in the source documents as prior medications.

Concomitant treatments are defined as treatments taken after study drug administration.

Prior and concomitant medications will be classified using the WHO-DRL drug dictionary (using the most recent version) and summarized overall by WHO Anatomical Therapeutic Chemical /ATC) Class and Preferred Term. All analyses will be based on the safety population.

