4.4. Handling of Drop-Outs or Missing Data

4.4.1. Missing or Partial Dates

The following imputation rules will be applied in case of partially missing information:

- Day missing => day will be replaced with 15
- Day and month missing => day and month will be replaced with July 1st
- Day, month and year missing => no imputation will be done.

Additional imputation rules for partial dates:

Prior, concomitant and steroid medications

Start date

When only the start day is missing, the last day of the month is imputed. When both day and month are missing, January 1st will be imputed. If day, month and year are missing no imputation will be done but medication will be assumed to be started before first intake.

End date

When only the end day is missing, the last day of the month is imputed. When both day and month are missing, December 31st will be imputed.

Sponsor: ITALFARMACO
Protocol: DSC/15/2357/53

If day, month and year missing no imputation will be done and medication will be assumed as concomitant medications.

Diagnosis date

When only the day is missing, the first day of the month is imputed. When both day and month are missing, January 1st will be imputed.

No imputation will be done if day, month and year are missing.

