6.4.3. Adverse Events

According on the onset date of the event, AEs will be defined as follows:

- Treatment-emergent AEs (TEAEs), those events with an onset date after study treatment initiation.
- Non-treatment-emergent AEs (non-TEAEs), those events with an onset date between informed consent and study treatment initiation.

An overview of TEAEs will be provided for the number of patients with any TEAEs, numbers of TEAEs, number of patients with serious TEAEs, number of serious TEAEs, number of patients with TEAEs leading to interruption of study treatment, number of patients with TEAEs leading to withdrawal of study treatment, number of patients with fatal TEAEs, number of patients with mild/moderate/severe TEAEs, number of patients with TEAEs related/not related to study treatment.

AEs for which relationship to study drug is not specified or unknown will be considered treatment related.

The incidence of TEAEs will be tabulated by System Organ Class (SOC) and Preferred Term (PT), and by SOC and PT and severity by treatment group. A subject with multiple occurrences of an AE will be counted only once in the AE category. These analysis will be repeated for all the above categories.

Sponsor: ITALFARMACO
Protocol: DSC/15/2357/53

TEAE will be summarized under the worst severity recorded for the event.

Deaths, SAEs and AEs leading to withdrawal of study treatment will also be listed.

Non-treatment emergent AEs will only be listed.

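### SAP 6.4.2 has no class for a drug started and stopped on study, and SAP 6.4.3 narrows the protocol's TEAE definition; SAP 1.1 declares neither change

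*SAP*

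**What the plan says.** **Medications.** SAP 6.4.2 has three classes. Prior means the drug ended before first intake. The other two are given as "concomitant (i.e. medications started before first intake and ongoing at the baseline) and steroid medications (used at baseline". The protocol sets no condition on the start date. Section 8.7.2 states "Concomitant treatments are defined as treatments taken after study treatment administration", and section 13.5 repeats it: "Concomitant treatments are defined as treatments taken after study drug administration". Section 8.7.2 also permits new treatment after screening ("supportive treatments such as antiemetics, antidiarrheals, antipyretics, anti-allergics, analgesics and antibiotics are allowed") and requires it to be captured: "Any medication or therapy that is taken by or administered to the patient during the study must be recorded in the eCRF". One further SAP rule bears on this. For medication end dates, SAP 4.4.1 says "If day, month and year missing no imputation will be done and medication will be assumed as concomitant medications".

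**Adverse events.** SAP 6.4.3 defines "Treatment-emergent AEs (TEAEs), those events with an onset date after study treatment initiation". Protocol 13.8 includes onset on the date of initiation as well as later. Under the SAP, events outside the definition drop out of the incidence tables: "Non-treatment emergent AEs will only be listed".

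**Declaring changes.** Protocol section 13 commits the SAP to describing any change to the planned analysis and the reason for it. SAP 1.1 lists five changes: the log-scale primary analysis, the MRI analysis, repeated-measures models for other secondary endpoints, the dystrophin variables, and the comparison of biopsy sites. Neither safety definition is among them.

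**The concern.** A concomitant medication table should show what patients took while on study drug. Followed as written, SAP 6.4.2 describes what they were already taking when they began. A course of an antibiotic or antiemetic begun and finished on study would be in the database but not in the table, so the output would not be the summary planned in protocol 13.5. Treatment for raised triglycerides, which protocol 8.8 allows during the study, is exposed to the same gap, although SAP 6.4.4 plans box-plots of triglycerides and total cholesterol by treatment group.

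The adverse event wording raises a separate, smaller question. If the derivation compares dates strictly, an event dated on the first dosing day is not treatment-emergent and appears only in a listing. The SAP also defines non-treatment-emergent events as falling between consent and initiation, without saying whether the end date is included. The choice is left to the programmer.

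**Working it through.** The plan gives no figure to reproduce here. The check applies each document's rules to the possible cases.

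**Medications.** Take a non-steroid drug with a known start date. A start is either before first intake or on/after it. An end is either recorded or wholly missing, which here stands for ongoing. That gives five patterns:

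| Pattern | Start | End | Protocol 8.7.2 / 13.5 | SAP 6.4.2 | SAP 4.4.1 missing-end rule |
|---|---|---|---|---|---|
| A | before first intake | before first intake | prior | prior | not applicable |
| B | before first intake | recorded, after first intake | concomitant | concomitant | not applicable |
| C | before first intake | wholly missing | concomitant | concomitant | concomitant |
| D | on/after first intake | recorded | concomitant | **no class** | not applicable |
| E | on/after first intake | wholly missing | concomitant | **no class** | concomitant |

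Counts:

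- Protocol concomitant: B, C, D, E = 4 of 5.
- Captured by SAP 6.4.2 alone: B, C = 2 of those 4.
- Captured by SAP 6.4.2 plus 4.4.1: B, C, E = 3 of 4.
- In no SAP class on any reading: D = 1.
- SAP sections giving different answers: E = 1.

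With first intake as day 1, a drug taken from day 30 to day 40 is concomitant under the protocol and unclassified under the SAP. A drug started on day 30 and still ongoing is unclassified under 6.4.2 but assumed concomitant if 4.4.1 is applied. Two drugs started on the same day can therefore be treated differently only because one has an end date.

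SAP 3.3.3 does not repair this. It refers to protocol 8.7.2 only for the lists of prohibited drugs and drugs requiring caution, not for the definition.

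**Adverse events.** SAP 4.2 makes the date of first dose study day 1 (event date − reference date + 1 = 1).

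| Onset | Protocol 13.8 (day ≥ 1) | SAP 6.4.3 read strictly (day > 1) |
|---|---|---|
| Day −1 | not treatment-emergent | not treatment-emergent |
| Day 1 | treatment-emergent | not treatment-emergent |
| Day 2 | treatment-emergent | treatment-emergent |

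The two definitions differ only for events dated on the day of first dose.

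**The case against.** **The adverse event wording may do no harm.** Protocol 12.7.2 sends events before the first intake to medical history and those after it to the adverse event section, so a first-day event on the adverse event page should already be post-dose. The safety endpoint in SAP section 2 counts treatment-emergent events from baseline. Both favour including first-day events. This stands as far as it goes: exclusion is a possible reading, not the established one. The two texts still differ, and one reading removes events from the tables.

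**SAP 4.4.1 may not conflict with 6.4.2.** Its end-date rule could be meant only to separate prior from concomitant among drugs begun before first intake. That is a fair reading. But pattern E then has no class either, and the SAP captures 2 of 4 rather than 3 of 4. The gap widens.

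**The ratios depend on how the patterns are drawn.** This is true, and they should not be read as frequencies. Partial dates are not shown separately, and treating an ongoing drug as one with no end date is an assumption about the eCRF. Pattern A is also not uniform: protocol 13.5 ties prior to the 6 months before screening, so a drug begun and stopped between screening and first intake fits poorly. None of this affects pattern D.

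**This may be a drafting slip, so there is no change to declare.** That may be so, but nothing in the documents corrects it, and a slip needs correcting just as an intended change needs declaring.

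**Conclusion.** The concern holds, as a minor point. The medication gap is certain on the text: a non-steroid drug started on or after first intake with a recorded end date has no class in SAP 6.4.2, while the protocol counts it as concomitant. The difference in the treatment-emergent definition is also certain as wording; its effect is only possible and limited to events dated on the first dosing day. SAP 1.1 declares neither.

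The effect is confined to descriptive tables. The primary analysis, power and efficacy tests are untouched. On-study drugs are still recorded in the eCRF, a prohibited drug may still appear among the protocol deviations summarised under SAP 6.1, and deaths, serious events and non-treatment-emergent events are still listed. The documents give no number of on-study drugs or first-day events, so neither size in patients nor direction by arm can be derived.

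**What to change.** - **SAP 6.4.2:** define concomitant as any medication taken on or after the first dose, including those started earlier and still ongoing. The missing-end-date rule in SAP 4.4.1 then agrees with it.
- **SAP 6.4.3:** define treatment-emergent as onset on or after the date of first dose, matching protocol 13.8.
- **SAP 1.1:** if either narrower definition is intended, list it there with its reason, as protocol section 13 requires.

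The cost is SAP wording and derivation code; no new data are needed. One side effect is that a pre-dose event entered on the adverse event page with the first-dose date would count as treatment-emergent. Protocol 12.7.2 directs such events to medical history, so this should arise only through an entry error.

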## 8.8 Treatment for hypertriglyceridemia

If a subject experiences an increase of triglycerides >ULN during the study, the investigator is allowed to prescribe adequate treatment including dietary supplements. These treatments will be reimbursed by the Sponsor.

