A box-plot will be produced for the following parameters over time by treatment group: platelets, hemoglobin, neutrophils, leukocytes, triglycerides and total cholesterol.

Pharmacokinetics

Finally, pharmacokinetic parameters (ITF2374 and ITF2375) for patients treated with givinostat will be listed by patient together with the IMP dosage. Further details will be provided in a separate SAP.

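### SAP 6.4.2 leaves medications started after the first dose out of every planned medication table, and is unclear on whether those tables are split by arm

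*SAP*

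**What the plan says.** SAP 6.4.2 sets three medication groups. Prior drugs ended before the first dose. The second group is described as "concomitant (i.e. medications started before first intake and ongoing at the baseline". The third is steroids, limited to those used at baseline. ATC class and preferred term results are then "summarized overall by WHO Anatomical Therapeutic Chemical /ATC) Class and Preferred Term".

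Protocol 8.7.2 and 13.5 define concomitant treatments by use after study drug administration. Section 13.5 then has them "summarized overall by WHO Anatomical Therapeutic Chemical /ATC) Class and Preferred Term. All analyses will be based on the safety population". SAP 1.1, which lists departures from the protocol's statistical methods, does not mention medications.

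Two other SAP statements bear on the arm split. Section 6.4 opens: "Safety analysis will be performed on the Safety Set and will be reported by actual treatment group". Section 6.4.1, on exposure, asks for results "on the Safety Analysis Set overall and by treatment group".

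On what may be taken, protocol 8.8 says that if triglycerides rise above ULN, "the investigator is allowed to prescribe adequate treatment including dietary supplements". The prohibited list in protocol 8.7.2 covers "Any pharmacologic treatment, other than corticosteroids, that might have an effect on" muscle strength or function, so corticosteroids are exempt.

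**The concern.** A medication table in a safety report should show what patients took while on study drug, by arm, so that the other by-arm results can be interpreted. Here the definition removes the drugs that matter most for that purpose: those begun after randomisation in response to something seen on study.

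Triglycerides are the clearest case. Amendment 2 treats raised triglycerides as an emerging signal, and the protocol lets investigators treat them. If such treatment works and is started more often in one arm, the triglyceride difference between arms shrinks, and nothing in the planned medication tables would explain why. Steroid starts or changes on study could act in a similar way on strength, function or histology. The documents give no sign of how often that happened.

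**Working it through.** The plan gives no figure on this point, so the check sets the texts side by side.

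**1. Where each course of medication falls.**

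| Course | SAP 6.4.2 | Protocol 8.7.2 and 13.5 |
|---|---|---|
| Ended before first dose | Prior | Prior, within the six-month look-back |
| Begun before first dose, continuing | Concomitant | Concomitant |
| Begun after first dose | No group | Concomitant |
| Steroid begun after first dose | No group | Concomitant |
| Baseline steroid, dose changed later | Baseline user; change not shown | Concomitant; change not shown by a class and term table |

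The two documents agree on the first two rows and part on the third and fourth. The last row is missed under either definition and needs a separate count.

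**2. Whether the affected drugs can occur.** Protocol 8.8 allows triglyceride treatment on study, and 8.7.2 exempts corticosteroids. Inclusion criterion 4 asks for stable steroid dosing in the six months before study treatment, and does not cover the period after it starts.

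**3. Where the information is needed.** SAP 6.4.4 summarises laboratory values by arm at each time point. It adds: "A box-plot will be produced for the following parameters over time by treatment group". Triglycerides and total cholesterol are on that list.

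**4. Pooled or by arm.** SAP 6.4.2 lies within 6.4, whose opening sentence calls for reporting by arm. Section 6.4.1 names both forms where both are wanted, while 6.4.2 names only the pooled one for the class and term summary. The sentence in 6.4.2 on patients with at least one medication names neither, so the 6.4 rule covers it. In the protocol, medications sit in 13.5, outside 13.8, which holds the by-arm safety rule. Two programmers could produce different tables from this text.

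**5. What kind of event these drugs are.** Baseline steroid use is the stratification factor (SAP 3.3.2) and a term in the primary ANCOVA (SAP 6.3.1) and in the ANCOVA and MMRM models for the secondary endpoints. Drugs begun after randomisation are intercurrent events: they can mask or mediate a difference between arms, but they do not confound a randomised comparison.

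**6. Size.** Amendment 2 reports a significant triglyceride increase in four patients, two of whom already had raised levels at baseline, leaving 4 − 2 = 2 without. The study was blinded at that point, so no arm is given. The same amendment added the hypertriglyceridaemia exclusion. The documents do not say how many patients were treated for raised triglycerides or changed steroids.

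**The case against.** The strongest reply is that the report would not be blind to these events. Protocol 12.7.2 requires laboratory abnormalities needing medical intervention to be recorded as adverse events, and SAP 6.4.3 tabulates those by arm. Triglycerides above 300 mg/dL call for interruption (protocol 7.3.1), and SAP 6.4.1 summarises dose modifications by arm. Protocol section 13 says that collected data will be listed. Since SAP 1.1 declares no change, one could also argue that the protocol definition still governs.

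Much of this stands, and it rules out saying that the report cannot reveal a problem. It does not supply the missing count. An adverse event term does not say whether a drug was given. The modification reasons in SAP 6.4.1 place adverse events, laboratory and ECG findings in one category. A steroid change need not be an adverse event at all. An undeclared contradiction also leaves the programmer with the SAP wording.

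Two stronger readings are tempting. One is that medications will be shown pooled only; the opening rule of SAP 6.4 prevents that conclusion, and the text is ambiguous. The other is that steroid use confounds the efficacy comparison. Baseline use is stratified and adjusted for, and the documents contain no evidence of differential steroid use on study.

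**Conclusion.** The definition in SAP 6.4.2 contradicts protocol 8.7.2 and 13.5 without being declared. Taken as written, it keeps every drug begun after the first dose out of the planned medication tables. The pooled wording is a second, smaller fault that needs clarifying; adding arm columns alone would not bring the omitted drugs back.

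This is a minor reporting gap. It does not touch the primary analysis. Its main effect is on the interpretation of by-arm triglycerides and, if steroids were started or changed on study, of function and histology. The conclusion assumes that the SAP wording is programmed literally. Any masking of a triglyceride difference further assumes that treatment was effective and was started unequally between arms, which the documents neither show nor exclude.

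**What to change.** In SAP 6.4.2:

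1. Restore the protocol definition, so that every medication taken after the first dose counts as concomitant. If a table of drugs in use at baseline is also wanted, label it as such and keep it separate.
2. State that prior, concomitant and steroid medications are summarised overall and by treatment group on the Safety Set.
3. Add a by-arm count of patients who start or change a triglyceride-lowering drug, and of those who start or change a corticosteroid, after the first dose. Place it beside the triglyceride summaries of SAP 6.4.4.

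The cost is one extra column per arm in a planned table and one short new table. Protocol 8.7.2 already requires dose, regimen, route, indication and dates for every medication in the eCRF, so nothing new has to be collected.
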